## Mini-Sentinel Assessment Protocol

### Parenteral Iron and Anaphylactoid Reactions

History of Modifications			
Version	Date	Modification	By
V2	10/25/2013	
 
• Additional information added to the Section I. BACKGROUND AND OBJECTIVES to include relevant literature (pages 1-3).
 
• Additional information regarding study limitations added to Section I.F. OBJECTIVE (page 5).
 
• Additional information regarding study limitations added to Section II., H. POTENTIAL LIMITATIONS AND ATTEMPTS TO MINIMIZE THEM, 1. Misclassification bias (pages 18-19).
 
	Parenteral Iron and Anaphylactoid Reactions Workgroup

## I. BACKGROUND AND OBJECTIVES

### A. PATHOPHYSIOLOGY AND INCIDENCE OF ANAPHYLAXIS AND ANAPHYLACTOID REACTIONS

The Summary Report of the Second National Institute of Allergy and Infectious Disease/Food Allergy and Anaphylaxis Network symposium defines anaphylaxis as “a serious allergic reaction that is rapid in onset and may cause death.” Anaphylactoid reactions are immediate systemic reactions which mimic anaphylaxis but are caused by non-IgE-mediated release of mediators from mast cells and basophils. They are also referred to as pseudoallergic drug reactions or non-allergic hypersensitivity reactions. Notably, hypersensitivity reactions to parenteral dextran therapy have been reported since the 1960s, and are attributed to dextran-reactive IgG antibodies. In general, symptoms of anaphylactoid reaction do not allow for discrimination between IgE-mediated anaphylaxis and non-IgE-mediated anaphylactoid reactions. Clinically, anaphylactoid reactions present and are treated identically to anaphylaxis.

Incidence rates of anaphylaxis reported in studies in U.S. populations vary greatly, ranging from approximately 10 to over 30 per 100,000 person-years. Discrepancies may be related to differences in the study populations, study design and case ascertainment methods, or the definition and criteria used to determine cases. Published studies have reported that approximately 11% to 17% of cases of anaphylaxis were attributed to administration of a medication, immunotherapy, or a diagnostic agent. While the risk of anaphylaxis is not well-known for most medications, evaluation of spontaneous reports has led to black box warnings for a number of medications (e.g. omalizumab, aprotinin, paclitaxel), as well as withdrawal of zomepirac sodium.

### B. EPIDEMIOLOGY OF IRON-INDUCED ANAPHYLAXIS/ANAPHYLACTOID REACTIONS

Parenteral iron is available as iron dextran, sodium ferric gluconate, iron sucrose, and ferumoxytol (Table 1). It is commonly used for the treatment of anemia in dialysis, malignancy, inflammatory bowel disease, and anemia due to ongoing blood losses (e.g., gastrointestinal bleeding, menorrhagia, postpartum bleeding). Few published studies have evaluated the risk of anaphylaxis associated with specific preparations of parenteral iron exposure. Only the iron dextran products have a black box warning regarding risk of anaphylactoid/anaphylaxis reactions and a test dose is recommended prior to parenteral administration of iron dextran.

**Table 1. Parenteral iron products**

Generic name	Trade name	Procedure codes	FDA approval date
Iron dextran	INFeD (low molecular weight), Dexferrum (high molecular weight)	J1750, J1751, J1752, J1760, J1770, J1780	Iron dextran-04/1957 INFeD-04/1974 Dexferrum-02/1996
Sodium ferric gluconate	Ferrlecit	J2915, 2916, S0098	02/1999

Generic name	Trade name	Procedure codes	FDA approval date
Iron sucrose	Venofer	J1755, J1756	11/2000
Ferumoxytol	Feraheme	Non ESRD-Q0138, ESRD dialysis-Q0139	06/2009

In a review of adverse events reported to the FDA between 2001 and 2003, Chertow *et al.* described 1,141 reported events associated with parenteral iron use. The study authors commented that compared to low molecular weight iron, life-threatening adverse drug events were more frequent among those given high molecular weight iron. They also noted that adverse drug events were less common among those given iron sucrose and sodium ferric gluconate.

Fletes *et al.* in 2001 described parenteral iron dextran related adverse events in dialysis patients using data from Fresenius Medical Care clinical variance reports. The study included serious adverse drug events (e.g., dyspnea) and other adverse drug events (e.g., vomiting, flushing, and pruritus). Among the 165 reported adverse drug events, dyspnea, hypotension, and neurological symptoms were the most common serious symptoms. Twenty-six percent required emergency department evaluation, 11% required admission, and one patient died. Adverse drug events were 8 times more common among users of one brand of iron dextran, Dexferrum, compared to another (INFeD). The study estimated a rate of suspected adverse drug events at 20 per 100,000 doses.

Mamula *et al.* in 2002 described parenteral iron dextran related adverse events in children with inflammatory bowel disease in a single-site chart review study. From 1994 to 2000, among 70 patients who received 119 infusions, 10 patients had immediate hypersensitivity reactions. None were life-threatening and no patients were admitted; 3 had hypotension requiring epinephrine treatment.

Barton *et al.* in 2000 performed a study of 135 iron-deficient patients with normal renal function who failed oral iron therapy and were treated with iron dextran; the patients were premedicated with cimetidine, diphenhydramine, and dexamethasone. No patients had anaphylaxis; 13% had mild reactions, including arthralgias and myalgias. Fishbane *et al.* in 1996 performed a study of 573 patients treated with iron dextran (INFeD) at four hemodialysis settings from 1993-1995; ten (1.7%) had anaphylactoid-type reactions.

Auerbach *et al.* in 2004 described an open-label, multicenter prospective randomized trial in 157 anemic patients receiving chemotherapy, comparing subcutaneous erythropoietin to (1) no iron; (2) oral iron; (3) iron dextran repeated bolus; (4) iron dextran infusion. There were 3 patients in the infusion group with adverse events – two delayed myalgia/arthralgia, and one acute hypersensitivity (the hypersensitivity reaction was in a patient receiving a test dose of Dexferrum). Of the bolus patients, one experienced delayed myalgia/arthralgia, one experienced fatigue, and one reported shortness of breath. In the oral iron group, one patient experienced nausea. Auerbach also describes the use of rapidly administered (1 hour) 1 gram low molecular weight iron dextran in 396 iron deficient patients, in which there were no anaphylactoid reactions and no serious adverse events.

Michael *et al.* in 2002 compared drug intolerance between sodium ferric gluconate and iron dextran in a multicenter, crossover, randomized, double blind, prospective study; the authors used placebo and historic controls. The authors found significantly less intolerance and serious adverse events in sodium ferric gluconate users compared to iron dextran controls. Another study by Coyne *et al.* in 2003 investigated adverse reactions to sodium ferric gluconate in iron dextran sensitive and iron dextran tolerant patients as part of a double blind, prospective, controlled trial of sodium ferric gluconate safety and tolerability. In 143 dextran sensitive patients, three had suspected allergic reactions to sodium ferric gluconate, including one serious reaction. These reactions included one patient with back pain and doubling of Tryptase levels (indicating an allergic reaction), one flushing and doubling of Tryptase levels, and one with dyspnea, hypotension, wheezing, and high baseline Tryptase levels. Because the latter patient had a decline in Tryptase after the event, this serious reaction was considered non-allergic. There were 5 suspected allergic reactions in the 2,194 iron dextran tolerant patients, which included four reactions (2 pruritis, 1 chills, 1 dyspnea and chest pain) without a change in Tryptase levels that were classified as non-allergic and one patient with rash where levels were not obtained.

Moniem and Bhandari in 2007 performed a crossover study among dialysis patients to compare the safety and efficacy of CosmoFer (an iron dextran; 144 patients; 2,294 doses) and VenoFer (an iron sucrose; 110 patients; 2,111 doses). There were no anaphylaxis events in either group. In order to compare the side effects and safety of low molecular weight iron dextran and iron sucrose, Sav *et al.* in 2007 recruited 30 patients in each group. All patients received a test dose before infusion. Eleven patients had an adverse reaction (including 1 with hypotension, no anaphylaxis) to iron dextran and 13 had an adverse reaction (including 2 cases with hypotension, no anaphylaxis) to iron sucrose. In another study comparing 979 doses of Cosmofer to 504 doses of Venofer, there were no cases of anaphylactoid-type reactions in either group. In a chart review study of adverse events among 329 users of low molecular weight iron dextran and iron sucrose, one patient receiving iron sucrose had an adverse reaction, which consisted of generalized pruritis.

Although the non-dextran intravenous (IV) iron products appear to be safer, severe anaphylactic-type reactions have been reported with all approved IV Iron products in adverse events reported to the FDA.

In a crossover study of 750 patients with chronic kidney disease not on dialysis who received ferumoxytol, one patient with a history of multiple drug allergies developed an anaphylactoid reaction and later recovered. Similarly, a phase III trial of ferumoxytol or oral iron in 304 patients with chronic kidney disease patients found no hypotension or hypersensitivity in the ferumoxytol group.

### C. VALIDITY OF ADMINISTRATIVE DATA TO IDENTIFY ANAPHYLAXIS

Few published studies have evaluated the validity of health plan administrative and claims data to identify anaphylaxis. These studies are summarized in the *Mini-Sentinel Systematic Evaluation of Health Outcome of Interest Definitions for Studies Using Administrative Data: Anaphylaxis Report*. In this report there were two studies which evaluated the validity of health plan administrative data to identify anaphylaxis and an additional study was published after the search results for the Mini-Sentinel report were completed.

Bohlke et al. identified potential cases of anaphylaxis occurring between 1991 and 1997 in a population of children and adolescents enrolled in Group Health Cooperative, a health maintenance organization in Washington State and a Mini-Sentinel Data Partner. Investigators reviewed the medical charts of all potential cases identified using diagnosis codes specific for anaphylaxis (e.g. International Classification of Diseases, 9th Revision, Clinical Modification [ICD-9-CM] code 995.0, other anaphylactic shock; ICD-9-CM 995.6, anaphylactic shock caused by adverse food reaction) and a sample of cases identified with other nonspecific codes (e.g. ICD-9-CM, 995.3, allergy unspecified). Administrative and claims data from hospitalizations, emergency department visits, and ambulatory encounters were assessed. The code with the highest positive predictive value (PPV) was ICD-9-CM 995.0, with 55% of potential cases confirmed to be a probable or possible case of anaphylaxis. The positive predictive values for nonspecific codes were much lower; for example, the positive predictive value for ICD-9-CM 995.3 (allergy unspecified) was 1%.

Johannes et al. evaluated the incidence of allergic reactions after exposure to antibiotics among members enrolled in a large U.S. health plan from July 2000 to June 2004. For patients with an emergency department or hospitalization claim for anaphylaxis (ICD-9-CM 995.0), medical record review was conducted. Sixteen of 28 patients (57%) with this code were confirmed to have anaphylaxis.

Iribarren et al. evaluated the validity of ICD-9-CM code 995.0 among a cohort of patients diagnosed with asthma and a comparison group of patients without asthma enrolled in Kaiser Permanente Northern California (also a Mini-Sentinel Data Partner) between 1996 and 2006. Administrative and claims data from hospitalizations, emergency department visits, and ambulatory encounters were assessed. Medical record review was conducted and cases were confirmed based upon the *Summary Report of the Second National Institute of Allergy and Infectious Disease/Food Allergy and Anaphylaxis Network symposium*. Of the 109 potential cases reviewed, 57 (52%) were confirmed as likely or probable cases.

The Mini-Sentinel Anaphylaxis Validation Workgroup developed and validated an algorithm consisting of diagnostic, symptom, and treatment codes in the Mini-Sentinel Distributed Database (MSDD). In a review of 122 patients for whom complete charts were received, 77 were judged by physician adjudicators to have anaphylaxis. The PPV for the algorithm was 63.1% (95% confidence interval [CI]: 53.9%-71.7%). The PPV was highest among inpatient visits with the ICD-9-CM codes 995.0 or 999.4. The workgroup report recommended chart review validation when using the algorithm in future medical product safety assessments, due to the low PPV.

#### **D. VALIDITY OF ADMINISTRATIVE DATA TO IDENTIFY PARENTERAL IRON**

An editorial in the *New England Journal of Medicine* by Auerbach and Rodgers in 2007 expressed concerns regarding potentially higher rates of adverse drug events among patients receiving high molecular weight iron dextran, and the difficulty of identifying high vs. low molecular weight iron dextran in claims data given the fact that both have the same name and the same billing code. Low molecular weight iron and the other iron products had lower rates of anaphylaxis according to the authors than high molecular weight iron.

## **E. SUMMARY OF BACKGROUND**

In summary, the epidemiology of parenteral iron-induced anaphylactoid or anaphylactic reactions is not well-described. Evidence from a large comparative safety study of the risk of anaphylaxis between various IV Iron products is lacking. Given the severity of the adverse drug reaction, and the potential difference in anaphylaxis among different products, a better understanding of the relative risk of anaphylaxis with use of iron dextran, compared to other iron products, is needed.

## **F. OBJECTIVE**

The objective of this proposal is to perform a one-time assessment of the association between parenteral iron products and anaphylactoid/anaphylaxis reactions. The FDA and workgroup recognize the potential limitations of the study, such as the limited ability to differentiate between high and low molecular weight iron products (described in detail in Section I), but believe the study will still produce useful information about the association in a large, diverse, population-based cohort. The results from this assessment are *not* expected to provide definitive evidence of a causal relation. They will be interpreted in the larger context of all that is known about the association from various sources, such as randomized controlled trials and post-market reports.

## **II. STUDY DESIGN AND METHODS**

### **A. DATA SOURCE**

This assessment will include all Mini-Sentinel Data Partners who can provide data to the analysis.

### **B. IDENTIFICATION OF NEW-USERS OF DRUGS OF INTEREST**

We propose to use a “new-user” cohort design. We will identify health plan members with a first administration of a parenteral iron preparation during the period January 1, 2000 to June 30, 2013. We note that not all Data Partners will have data for the entire study period. Use of parenteral iron preparations will be identified using the procedure codes shown in Table 1. We will not identify parenteral iron administration using the National Drug Codes (NDCs), because in a summary table analysis we found the use of IV iron products identified as by NDCs in the Mini-Sentinel Distributed Database to be quite low (~3,000 vs. ~200,000 identified by procedure codes, see Section H). Given that anaphylaxis is a rare event, we decided that this number is too low to identify an adequate number of events among users.

We refer to the procedure date of the first administration of the iron preparation as the *index date*. We will require eligible individuals to meet all of the following criteria during the 183-day period prior to the index date: 1) continuous health plan enrollment with pharmacy and medical benefits; and 2) no administration of any of the parenteral iron products of interest in the emergency department, outpatient (ambulatory) visits, or inpatient visits; and (3) no procedure codes for dialysis (Appendix 1). Dialysis patients were excluded from analysis because they represent less than half of the population receiving parenteral iron in the MSDD, their prescribing patterns appear different from other parenteral iron users, and because dialysis patients may be clinically distinct from other parenteral iron users. Gaps of 45 days or less in enrollment will be ignored because they usually represent administrative gaps rather than actual disenrollment.

The exposure group will be new users of iron dextran. The comparison group will be new users of other parenteral iron products. We will identify use of iron preparations in the inpatient, emergency department, and outpatient settings, although we expect the majority of parenteral iron use to be in the outpatient setting. For patients who may be eligible for more than one new use episode during the study period, only their first eligible episode will be included in the analysis.

### **C. IDENTIFICATION OF OUTCOME OF INTEREST**

We will employ the algorithm developed by the Mini-Sentinel Anaphylaxis Validation Workgroup to identify potential cases of anaphylaxis using health plan data (Appendices 2 and 3). We will identify cases of potential anaphylaxis occurring on the day of or the day after exposure to parenteral iron. Because we expect that the number of cases identified will be small, we will further include a more sensitive algorithm that will identify patients who received epinephrine the same day or the day after being administered parenteral iron. We will review these epinephrine cases using the same methods as anaphylaxis cases. Chart abstractors and adjudicators will be blinded to whether cases were identified using the anaphylaxis algorithm or from epinephrine administration.

#### D. CHART REVIEW VALIDATION OF CASES OF POTENTIAL ANAPHYLAXIS

The chart review will follow an approach modified from the previous Mini-Sentinel validation studies, including: (1) identification of a clinical definition for anaphylaxis for use with medical records data; (2) identification, retrieval, and de-identification of medical records of patients who have been identified by Data Partners utilizing the algorithm for anaphylaxis (Table 2); (3) chart abstraction by a trained abstractor using a structured abstraction form; and (4) adjudication of anaphylaxis cases based on physician review of the completed data abstraction forms.

We will obtain all relevant portions of the medical record. The record will be redacted, abstracted, and reviewed. Because the number of anaphylaxis cases will likely be small, the goal is to validate all potential cases. Two physicians will review abstracted information and, if they feel it necessary, redacted charts and make judgments about whether anaphylaxis occurred. They will use the clinical definition developed by a recent consensus group and published by Sampson *et al.* as the gold standard for determining whether anaphylaxis occurred. Only events classified as cases of anaphylaxis, determined based on the clinician definition developed by Sampson *et al.* will be in the primary analysis (Table 2).

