**Table 2. Clinical criteria for diagnosing anaphylaxis for use in primary analysis**

Anaphylaxis is highly likely when any of the following 3 criteria are fulfilled:

1. Acute onset of an illness (minutes to several hours) with involvement of the skin, mucosal tissue, or both (e.g., generalized hives, pruritus or flushing, swollen lips-tongue-uvula) AND AT LEAST ONE OF THE FOLLOWING:
 
 
a. Respiratory compromise (e.g., dyspnea, wheeze-bronchospasm, stridor, reduced peak expiratory flow, hypoxemia)
 
b. Reduced blood pressure or associated symptoms of end-organ dysfunction (e.g., hypotonia [collapse], syncope, incontinence)
 

2. Two or more of the following that occur rapidly after exposure to a likely allergen for that patient (minutes to several hours):
 
 
a. Involvement of the skin-mucosal tissue (e.g., generalized hives, itch-flush, swollen lips-tongue uvula)
 
b. Respiratory compromise (e.g., dyspnea, wheeze-bronchospasm, stridor, reduced peak expiratory flow, hypoxemia)
 
c. Reduced blood pressure or associated symptoms (e.g., hypotonia [collapse], syncope, incontinence)
 
d. Persistent gastrointestinal symptoms (e.g., crampy abdominal pain, vomiting)
 

3. Reduced blood pressure after exposure to known allergen for that patient (minutes to several hours):
 
 
a. Infants and children: low systolic blood pressure (age specific) or greater than 30% decrease in systolic blood pressure*
 
b. Adults: systolic blood pressure of less than 90 mm Hg or greater than 30% decrease from that person's baseline blood pressure
 

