**ICD-9-CM procedure code:**

99.60 = CPR

a International Classification of Diseases, Ninth Revision, Clinical Modification

b Healthcare Common Procedure Coding System

c Current Procedural Terminology

**C. APPENDIX 3. FINAL ALGORITHM FROM THE MINI-SENTINEL ANAPHYLAXIS VALIDATION WORKGROUP TO IDENTIFY POTENTIAL CASES OF ANAPHYLAXIS USING ICD-9-CM DATA.**

**Criterion A:** (995.0 [other anaphylactic shock] or 999.4 [anaphylactic shock due to serum]) inpatient or emergency department encounter

**OR**

**Criterion B:** (995.0 [other anaphylactic shock] or 999.4 [anaphylactic shock due to serum]) outpatient encounter **PLUS** a code for one of the following symptoms/procedures/treatments:

- i. bronchospasm (519.11) or
- ii. stridor (786.1) or
- iii. hypotension (458.9) or
- iv. epinephrine (J0170 or J0171) OR
- v. injection of diphenhydramine (J1200) or
- vi. CPR (92950 or 99.60)

**OR**

**Criterion C:** (995.3 [allergy unspecified] or 995.2 [other unspecified adverse effect of drug] or E930-E949 [drugs, medicinal and biological substances causing adverse effects in therapeutic use]) inpatient or emergency department encounter

- i. **PLUS** a code for one of the following symptoms/procedures/treatments:
  1. bronchospasm (519.11) or
  2. stridor (786.1) or
  3. injection of diphenhydramine (J1200)
- ii. **and ALSO** a code for one of the following symptoms/procedures/treatments:
  1. hypotension (458.9) or
  2. epinephrine (J0170 or J0171) or
  3. CPR (92950 or 99.60)

For inpatient and ED codes: All patients who met inclusion criteria were sampled.

For outpatient encounters: All patients who met inclusion criteria, excluding patients with an encounter in the prior 30 days that documented an anaphylaxis code (995.0 or 999.4) were sampled.

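### The primary outcome counts any confirmed anaphylaxis on day 0 or day 1, with no stated check that it began after the iron or that iron is the likely cause

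*Protocol*

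**What the plan says.** Section II.C looks for potential cases "occurring on the day of or the day after exposure to parenteral iron". Section II.F starts follow-up on the index date and ends it one day later at the latest. Both are calendar-day rules and set no order within the day.

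In section II.D, two physicians "make judgments about whether anaphylaxis occurred". The entry rule for the primary analysis is "Only events classified as cases of anaphylaxis, determined based on the clinician definition developed by Sampson" and colleagues (Table 2). The three criteria treat exposure differently:

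- Criterion 1 opens with "Acute onset of an illness (minutes to several hours) with involvement of the skin, mucosal tissue, or both" and names no exposure.
- Criterion 2 requires "Two or more of the following that occur rapidly after exposure to a likely allergen for that patient (minutes to several hours", without saying that the allergen is the iron.
- Criterion 3 requires low blood pressure after a known allergen, again not necessarily the iron.

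The secondary adjudication (Table 3) grades severity, not cause. Section II.H.1 adds product blinding, the dextran brand where it can be found, and premedication. It names no other suspect drug and no onset time.

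Chemotherapy encounter is a listed indication (Table 6). The propensity score uses the Table 5 covariates, which include neither chemotherapy nor indication. Section II.H.2 expects indication to be descriptive only.

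**The concern.** The objective is the association between iron products and anaphylaxis. Under the stated rule, a true anaphylaxis that began before the infusion, or that another agent caused, is charged to whichever iron product the patient received. Chart review as described does not remove it, because it is not a false positive under Table 2.

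The setting makes this plausible. Cases are sought in inpatient, emergency and outpatient care. The cohort includes chemotherapy patients. Section I.A itself refers to "black box warnings for a number of medications (e.g. omalizumab, aprotinin, paclitaxel" and others. Any epinephrine given on day 0 or day 1 triggers review, and Appendix 3 accepts general drug-adverse-effect codes when paired with symptom and treatment codes.

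Two planned results are exposed. The absolute incidence (section II.G.3) would be too high as a measure of iron reactions. The odds ratio (section II.G.5) would be distorted in a direction that depends on how other-cause events fall between the groups. Events are expected to be few, so a handful of charts matters.

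**Working it through.** **Inputs from the protocol.** Section II.G.7 gives 40,015 dextran users, 60,714 users of other iron, a 0.05 significance level and a relative risk (RR) of 4 as the value that would influence policy. Table 7 gives a lowest baseline of 2.05 per 10,000. Section I.A gives community anaphylaxis of about 10 to over 30 per 100,000 person-years. **Assumed, not in the protocol:** f, the share of comparator events with a cause other than iron, and k, the dextran-to-comparator ratio of other-cause risk.

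**Step 1: reproduce Table 7.** Exact power of Fisher's test, two-sided 0.05 (p-value as twice the one-sided tail), at baseline 2.05 and RR 2.80 is 80.7%, against the stated 81.3%. All 12 rows agree within 0.7 percentage points. The power table is not at fault.

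**Step 2: rule out community background.** Over two days, 10 to 30 per 100,000 person-years is (1 to 3 per 10,000) × 2/365.25, or about 0.005 to 0.016 per 10,000. Against 2.05 that is at most 0.016/2.05 = 0.8%. Only agents given around the infusion could matter.

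**Step 3: expected counts.** Comparator events: 60,714 × 2.05/10,000 = 12.4. If f = 30%, about 0.3 × 12.4 = 3.7 of them have another cause. The same risk (0.3 × 2.05 = 0.615 per 10,000) gives 40,015 × 0.615/10,000 = 2.5 events among dextran users.

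**Step 4: effect on the RR.** Table 7's baselines come from the feasibility programs, and no attribution to a cause is described for them. The total comparator risk is therefore held at 2.05 and split into iron and other causes:

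observed RR = RR × (1 − f) + f × k

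With k = 1 and a true RR of 4:

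| f (assumed) | Observed RR | Power at baseline 2.05 |
|---|---|---|
| 0% | 4.0 | 99.0% |
| 10% | 4 × 0.9 + 0.1 = 3.7 | 97.6% |
| 20% | 4 × 0.8 + 0.2 = 3.4 | 94.8% |
| 30% | 4 × 0.7 + 0.3 = 3.1 | 89.6% |
| 50% | 4 × 0.5 + 0.5 = 2.5 | 67.6% |

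**Step 5: unequal other-cause risk, f = 30%.**

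| k (assumed) | True RR 1 reads as | True RR 4 reads as |
|---|---|---|
| 0.5 | 0.7 + 0.15 = 0.85 | 2.8 + 0.15 = 2.95 |
| 2 | 0.7 + 0.6 = 1.30 | 2.8 + 0.6 = 3.40 |
| 5 | 0.7 + 1.5 = 2.20 | 2.8 + 1.5 = 4.30 |

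The ratio can move away from 1 under a true null.

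**Step 6: effect on incidence.** Comparator incidence exceeds its iron-caused part by 1/(1 − f): 1.11, 1.25, 1.43 and 2.00 for f of 10%, 20%, 30% and 50%. This happens whether or not the groups are balanced.

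**The case against.** The strongest case against is that all-cause confirmed anaphylaxis in a two-day window, with an active comparator and product-blinded double review, is a usable comparative endpoint. The protocol disclaims definitive causal evidence. Criteria 2 and 3 already demand onset within minutes to hours of a likely or known allergen. The abstraction form and any separate analysis plan are not shown and may record onset time and concurrent drugs. This much stands: the point is a gap in specificity, not a contradiction or a miscalculation. A form field alone would still not settle which events count, because section II.D fixes the entry rule as the Table 2 criteria.

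Four stronger readings are tempting and not supported:

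- **That the RR is always pulled toward 1.** This needs equal other-cause risk in both groups. Product blinding makes judging errors similar but does not equalise co-treatment. The score captures some agents through immunosuppressive therapy (cyclophosphamide and rituximab, for example), but not chemotherapy as such.
- **That 2.05 per 10,000 is an iron-caused risk to which other events are added.** Nothing in section II.G.7 makes it cause-specific, which is why Step 4 splits it.
- **That transfusion reactions are a documented source.** Blood products as a co-exposure appear nowhere in the protocol. The code "999.4 [anaphylactic shock due to serum" is only a screening code, followed by chart review. Likewise the boxed-warning examples in section I.A do not show co-administration with iron.
- **That the protocol deliberately counts reactions before the infusion.** It says nothing either way. The point is that the stated window and criterion 1 would admit them.

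**Conclusion.** The concern holds in a limited form. As written, a Table 2 anaphylaxis on day 0 or day 1 counts as an event for the iron product even if it began before the iron or another agent caused it. Incidence would be overstated. The RR would move toward 1 if other-cause risk is equal in the two groups, and could move either way if not.

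The size is unknown. Under equal risk and assumed shares of 10% to 50%, a true RR of 4 reads as 3.7 to 2.5. Power to detect it at the lowest Table 7 baseline stays near 90% up to a 30% share. The main risk is therefore a misread magnitude against the threshold of 4, more than a missed signal. These figures rest on assumed f and k and on a total comparator risk of 2.05 per 10,000. General-population background is not part of the problem. This is a worthwhile improvement to the outcome definition, not a fatal flaw.

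**What to change.** Add two items to the abstraction and adjudication forms, keeping adjudicators blinded to the iron product:

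1. Did the reaction begin before or after the start of iron, or is this not recorded?
2. Is another agent given around the infusion the more likely cause?

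State in section II.D that events with onset before the iron are not counted, and say how charts with no recorded time are handled. Keep the all-cause result as primary. Pre-specify one sensitivity analysis, for both the incidence and the odds ratio, restricted to events not attributed to another agent. In section II.H.1, note that other-cause events raise the incidence and can move the ratio toward 1 or either way, depending on balance.

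The cost is two fields on charts already being read and one extra analysis. Settling this before adjudication avoids reopening charts and attributing cause after the results are known. The downside is that attribution is a judgment and the restricted analysis has fewer events, so it belongs beside the all-cause result and not in its place.
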